8.6 Safety Review Committee (SRC)

In the Phase 1 portion of the study, safety will be reviewed by a Safety Review Committee (SRC) consisting of the Medical Monitor, the Principal Investigators, and additional designees by the Sponsor or the site Principal Investigators. After Phase 1, safety will be reviewed by the safety review committee (SRC) before proceeding to Phase 2.

In Phase 2, the Sponsor will perform routine reviews of the safety data at an interval no less than quarterly and after the 20th randomized subject reaches the 30-day follow up timepoint, whichever occurs first.

8.7 Interim Analysis

During the Phase 2 portion of the study, an unblinded interim analysis will be performed after 6- month follow-up data are available for the first 20 randomized subjects (i.e., roughly 30 percent of the planned enrollment of 66 subjects in Phase 2), for the purposes of assessing preliminary efficacy.

Appendix 1: Regulatory, Ethical, and Study Oversight Considerations

Regulatory and Ethical Considerations

This study will be conducted in accordance with the protocol and with the following:

- Consensus ethical principles derived from international guidelines including the Declaration of Helsinki and Council for International Organizations of Medical Sciences (CIOMS) International Ethical Guidelines
- Applicable International Council for/Conference on Harmonization (ICH) Good Clinical Practice (GCP) Guidelines
- Applicable laws and regulations

The protocol, protocol amendments, ICF, Investigator's Brochure, and other relevant documents (e.g, participant recruitment advertisements) must be submitted to an Institutional Review Board (IRB)/Independent Ethics Committee (IEC) by the investigator and reviewed and approved by the IRB/IEC before the study is initiated.

Any amendments to the protocol will require IRB/IEC approval before implementation of changes made to the study design, except for changes necessary to eliminate an immediate hazard to study participants.

The investigator will be responsible for the following:

- Providing written summaries of the status of the study to the IRB/IEC annually or more frequently in accordance with the requirements, policies, and procedures established by the IRB/IEC
- Notifying the IRB/IEC of SAEs or other significant safety findings as required by IRB/IEC procedures
- Providing oversight of the conduct of the study at the site and adherence to requirements of 21 CFR, ICH guidelines, the IRB/IEC, European regulation 536/2014 for clinical studies (if applicable), and all other applicable local regulations

Financial Disclosure

Investigators and sub-investigators will provide the sponsor with sufficient, accurate financial information, as requested, to allow the sponsor to submit complete and accurate financial certification or disclosure statements to the appropriate regulatory authorities. Investigators are responsible for providing information on financial interests during the course of the study and for 1 year after completion of the study.

Informed Consent Process

In accordance with regulatory and local IRB/IEC/REB requirements, before study procedures are performed, subjects will be informed about the study and required to sign the IRB/IEC/REB approved ICF. This form will be signed after adequate explanation of the aims, methods, objective and potential hazards of the study and prior to undertaking any study-related procedures. The Sponsor or its designee will provide an ICF template to the investigator. The Sponsor or its designee must approve changes to the ICF template prior to submission to the IRB/IEC/REB. Informed consent will be obtained according to the applicable IRB/IEC/REB requirements. No patient is to be screened or treated until an ICF, written in a language in which the patient is fluent, has been obtained. The signed ICF will be retained with the study records. Each patient will also be given a copy of his/her signed ICF.

Data Protection

Participants will be assigned a unique identifier by the sponsor. Any participant records or datasets that are transferred to the sponsor will contain the identifier only; participant names or any information that would make the participant identifiable will not be transferred.

The participant must be informed that his/her personal study-related data will be used by the sponsor in accordance with local data protection law. The level of disclosure must also be explained to the participant who will be required to give consent for their data to be used as described in the informed consent.

The participant must be informed that his/her medical records may be examined by Clinical Quality Assurance auditors or other authorized personnel appointed by the sponsor, by appropriate IRB/IEC members, and by inspectors from regulatory authorities.

Data Quality Assurance

All participant data relating to the study will be recorded on printed or eCRFs unless transmitted to the sponsor or designee electronically (eg, laboratory data). The investigator is responsible for verifying that data entries are accurate and correct by physically or electronically signing the CRF.

The investigator must maintain accurate documentation (source data) that supports the information entered in the CRF.

The investigator must permit study-related monitoring, audits, IRB/IEC review, and regulatory agency inspections, and provide direct access to source data documents.

The sponsor or designee is responsible for the data management of this study including quality checking of the data.

The sponsor assumes accountability for actions delegated to other individuals (eg, Contract Research Organizations).

Study monitors will perform ongoing source data verification to confirm that data entered into the CRF by authorized site personnel are accurate, complete, and verifiable from source documents; that the safety and rights of participants are being protected; and that the study is

being conducted in accordance with the currently approved protocol and any other study agreements, ICH GCP, and all applicable regulatory requirements.

Source Documents

Source documents include but are not limited to original documents, data and records such as hospital/ medical records (including electronic health records), clinic charts, lab results, subject diaries, data recorded in automated instruments, microfilm or magnetic media, and pharmacy records, etc. At a minimum, all data required to be collected by the protocol should have supporting source documentation for entries in the eCRF, unless the protocol specifies that data can be recorded directly on/in the eCRF or other device.

Study and Site Start and Closure

The study start date is the date on which the clinical study will be open for recruitment of participants.

The sponsor designee reserves the right to close the study site or terminate the study at any time for any reason at the sole discretion of the sponsor. Study sites will be closed upon study completion. A study site is considered closed when all required documents and study supplies have been collected and a study-site closure visit has been performed.

The investigator may initiate study-site closure at any time, provided there is reasonable cause and sufficient notice is given in advance of the intended termination.

Reasons for the early closure of a study site by the sponsor or investigator may include but are not limited to:

- Failure of the investigator to comply with the protocol, the requirements of the IRB/IEC or local health authorities, the sponsor's procedures, or GCP guidelines
- Inadequate recruitment of participants by the investigator
- Discontinuation of further study intervention development

If the study is prematurely terminated or suspended, the sponsor will promptly inform the investigators, the IECs/IRBs, the regulatory authorities, and any contract research organization(s) used in the study of the reason for termination or suspension, as specified by the applicable regulatory requirements. The investigator will promptly inform the subject and must ensure appropriate subject therapy and/or follow-up

Publication Policy

- The results of this study may be published or presented at scientific meetings. If this is foreseen, the investigator agrees to submit all manuscripts or abstracts to the sponsor before submission. This allows the sponsor to protect proprietary information and to provide comments.

- The sponsor will comply with the requirements for publication of study results. In accordance with standard editorial and ethical practice, the sponsor will generally support publication of multicenter studies only in their entirety and not as individual site data. In this case, a coordinating investigator will be designated by mutual agreement.
- Authorship will be determined by mutual agreement and in line with International Committee of Medical Journal Editors authorship requirements.

Appendix 2: Clinical Laboratory Tests

The tests detailed in Table will be performed by the local laboratory per the SoA. Abnormal clinically significant local laboratory results collected outside of the protocol should be captured as Adverse Events.

Protocol-specific requirements for inclusion or exclusion of participants are detailed in Section 5 of the protocol. Additional tests may be performed at any time during the study as determined necessary by the investigator or required by local regulations.

Table 5 Protocol-Required Safety Laboratory Assessments

Hematology/CBC	Biochemistry	Other
ANC Hemoglobin Hematocrit Red blood cell (RBC) Count White blood cell (WBC) count Platelet Count WBC Differential	Blood urea nitrogen (BUN) Creatinine Creatinine clearance Glucose Potassium Sodium Calcium Chloride CO ₂ Inorganic phosphate Aspartate Aminotransferase (AST) Alanine Aminotransferase (ALT) Gamma-glutamyl transferase (GGT) Total bilirubin (direct bilirubin reflex if elevated) Albumin Alkaline phosphatase (ALP) Uric acid	INR/PTT (SCRN only)

Appendix 3: Adverse Events: Definitions and Procedures for Recording, Evaluating, Follow-up, and Reporting

Definition of Adverse Event

AE Definition

An AE is any untoward medical occurrence in a patient or clinical investigation subject administered a pharmaceutical product and which does not necessarily have a causal relationship with this treatment. An AE can therefore be any unfavorable and unintended sign (including an abnormal laboratory finding), symptom, or disease temporally associated with the use of a medicinal (investigational) product, whether or not related to the medicinal (investigational) product.

-

Events Meeting the AE Definition

- Any abnormal laboratory test results (such as hematology, clinical chemistry) or other safety assessments (e.g., ECG, radiological scans, vital signs measurements), including those that worsen from baseline, considered clinically significant in the medical and scientific judgment of the investigator (i.e., not related to progression of underlying disease).
- Exacerbation of a chronic or intermittent pre-existing condition including either an increase in frequency and/or intensity of the condition.
- Any new condition detected or diagnosed after study intervention administration even though it may have been present before the start of the study.
- Signs, symptoms, or the clinical sequelae of a suspected drug-drug interaction, including investigational product with a concomitant medication.
- Signs, symptoms, or the clinical sequelae of a suspected overdose of either study intervention or a concomitant medication. Overdose per se will not be reported as an AE/SAE unless it is an intentional overdose taken with possible suicidal/self-harming intent. Such overdoses should be reported regardless of sequelae.
- For situations when an AE or SAE is due to NSCLC report all known signs and symptoms. Death due to disease progression in the absence of signs and symptoms should be reported as the primary tumor type (e.g., metastatic NSCLC). Note: The term “disease progression” should not be used to describe the DRE or AE.

Events NOT Meeting the AE Definition

- Any clinically significant abnormal laboratory findings or other abnormal safety assessments that are associated with the underlying disease, unless judged by the investigator to be more severe than expected for the participant’s condition.

- The disease/disorder being studied or expected progression, signs, or symptoms of the disease/disorder being studied, unless more severe than expected for the participant's condition.
- Medical or surgical procedure (e.g., endoscopy, appendectomy): the condition that leads to the procedure is the AE.
- Situations in which an untoward medical occurrence did not occur (social and/or convenience admission to a hospital).
- Anticipated day-to-day fluctuations of pre-existing disease(s) or condition(s) present or detected at the start of the study that do not worsen.

Definition of Serious Adverse Event

If an event is not an AE per definition above, then it cannot be an SAE even if serious conditions are met (e.g., hospitalization for signs/symptoms of the disease under study, death due to progression of disease).

An SAE is defined as any untoward medical occurrence that, at any dose:

- **Results in death**
- **Immediately life threatening**

The term 'life threatening' in the definition of 'serious' refers to an event in which the participant was at risk of death at the time of the event. It does not refer to an event that hypothetically might have caused death if it were more severe.

- **Requires inpatient hospitalization or prolongation of existing hospitalization**

In general, hospitalization signifies that the participant has been detained (usually involving at least an overnight stay) at the hospital or emergency ward for observation and/or treatment that would not have been appropriate in the physician's office or outpatient setting. Complications that occur during hospitalization are AEs. If a complication prolongs hospitalization or fulfills any other serious criteria, the event is serious. When in doubt as to whether "hospitalization" occurred or was necessary, the AE should be considered serious.

Hospitalization for elective treatment of a pre-existing condition that did not worsen from baseline is not considered an AE.

- **Results in persistent disability/incapacity**

- The term disability means a substantial disruption of a person's ability to conduct normal life functions.
- This definition is not intended to include experiences of relatively minor medical significance such as uncomplicated headache, nausea, vomiting, diarrhea, influenza, and accidental trauma (eg, sprained ankle) that may interfere with or prevent everyday life functions but do not constitute a substantial disruption.

- **Is a congenital anomaly/birth defect**

- **Other medically important serious event:**

- Medical or scientific judgment should be exercised in deciding whether SAE reporting is appropriate in other situations such as important medical events that may not be immediately life threatening or result in death or hospitalization but may jeopardize the participant or may require medical or surgical intervention to prevent one of the other outcomes listed in the above definition. These events should usually be considered serious. Examples of such events include invasive or malignant cancers, intensive treatment in an emergency room or at home for allergic bronchospasm, blood dyscrasias or convulsions that do not result in hospitalization, or development of drug dependency or drug abuse.

Recording and Follow-Up of Adverse Events and/or Serious Adverse Events

AE and SAE Recording

- When an AE/SAE occurs, it is the responsibility of the investigator to review all documentation (e.g., hospital progress notes, laboratory reports, and diagnostics reports) related to the event.
- The investigator will then record all relevant AE/SAE information in the CRF.
- It is **not** acceptable for the investigator to send photocopies of the participant's medical records to Galera Therapeutics in lieu of completion of the AE/SAE CRF page.
- There may be instances when copies of medical records for certain cases are requested by Galera Therapeutics. In this case, all participant identifiers, with the exception of the participant number, will be redacted on the copies of the medical records before submission to Galera Therapeutics.
- The investigator will attempt to establish a diagnosis of the event based on signs, symptoms, and/or other clinical information. Whenever possible, the diagnosis (not the individual signs/symptoms) will be documented as the AE/SAE.
- The investigator must assign the following AE attributes:
 - o AE diagnosis or syndrome(s), if known (if not known, signs or symptoms);
 - o Dates of onset and resolution (if resolved);
 - o Severity (or toxicity defined below);
 - o Assessment of relatedness to GC4711, SBRT; and
 - o Action taken.

Severity/Grading of Adverse Events

The investigator will make an assessment of intensity for each AE and SAE reported during the study using NCI CTCAE grading scale, Version 5.0.

Assessment of Causality

- The investigator is obligated to assess the relationship between study intervention and each occurrence of each AE/SAE.
- A “reasonable possibility” of a relationship conveys that there are facts, evidence, and/or arguments to suggest a causal relationship, rather than that a relationship cannot be ruled out.
- The investigator will use clinical judgment to determine the relationship.
- Alternative causes, such as underlying disease(s), concomitant therapy/treatments, and other risk factors, as well as the temporal relationship of the event to study intervention administration, will be considered and investigated.
- The investigator will also consult the Investigator’s Brochure (IB) and/or Product Information, for marketed products, in his/her assessment.
- For each AE/SAE, the investigator **must** document in the medical notes that he/she has reviewed the AE/SAE and has provided an assessment of causality.
- There may be situations in which an SAE has occurred, and the investigator has minimal information to include in the initial report to Galera Therapeutics. However, **it is very important that the investigator always makes an assessment of causality for every event before the initial transmission of the SAE data to Galera Therapeutics.**
- The investigator may change his/her opinion of causality in light of follow-up information and send an SAE follow-up report with the updated causality assessment.
- The causality assessment is one of the criteria used when determining regulatory reporting requirements.

Follow-up of AEs and SAEs

- The investigator is obligated to perform or arrange for the conduct of supplemental measurements and/or evaluations as medically indicated or as requested by Galera Therapeutics to elucidate the nature and/or causality of the AE or SAE as fully as possible. This may include additional laboratory tests or investigations, histopathological examinations, or consultation with other health care professionals.
- New or updated information will be recorded in the originally completed CRF.
- The investigator will submit any updated SAE data to Galera Therapeutics within 24 hours of receipt of the information.

Reporting of SAEs

SAE Reporting to IQVIA Safety

All SAEs should be submitted in compliance with the reporting requirements and timelines per the SAE Report Form Completion Guidelines.

Appendix 4: Relationship Between National Cancer Institute – Common Terminology Criteria for Adverse Events, Version 5.0 and Radiographic Pneumonitis/Fibrosis Criteria (Kimura IJROB 2006)

Subjects will be evaluated radiographically for presence of the described items listed in the table below. The Grade and p-value columns are included only as a reference to the relationship between CTCAE grading of pneumonitis and the presence of the descriptors and do not need to be considered when collecting subject data.

	Grade 1*	Grade 2*	Grade 3*	Total	p value††
Acute radiation pneumonitis					
Diffuse consolidation	3	11	2	16	0.000675
Patchy consolidation and GGO	6	2	0	8	0.175
Diffuse GGO	4	2	0	6	0.479
Patchy GGO	0	1	0	1	0.286
No evidence of increased density	12	3	1	16	0.0314
Radiation fibrosis					
Modified conventional pattern	12	14	1	27	0.0394
Mass-like pattern	4	3	2	9	0.559
Scar-like pattern	9	2	0	11	0.0297
Total	25	19	3	47	

Abbreviation: GGO = ground-glass opacity.

Appendix 5: Contraceptive Guidance and Collection of Pregnancy Information

Definitions:

Woman of Childbearing Potential (WOCBP)

A woman is considered fertile following menarche and until becoming post-menopausal unless permanently sterile (see below).

If fertility is unclear (eg, amenorrhea in adolescents or athletes) and a menstrual cycle cannot be confirmed before first dose of study intervention, additional evaluation should be considered.

Women in the following categories are not considered WOCBP

- Premenarchal
- Premenopausal female with 1 of the following:
- Documented hysterectomy
- Documented bilateral salpingectomy
- Documented bilateral oophorectomy

For individuals with permanent infertility due to an alternate medical cause other than the above, (eg, mullerian agenesis, androgen insensitivity), investigator discretion should be applied to determining study entry.

Note: Documentation can come from the site personnel's: review of the participant's medical records, medical examination, or medical history interview.

- Postmenopausal female
- A postmenopausal state is defined as no menses for 12 months without an alternative medical cause.

Male participants with partners who become pregnant

The investigator will attempt to collect pregnancy information on any male participant's female partner who becomes pregnant while the male participant is in this study. This applies only to male participants who receive GC4711.

After obtaining the necessary signed informed consent from the pregnant female partner directly, the investigator will record pregnancy information on the appropriate form and submit it to the sponsor within 24 hours of learning of the partner's pregnancy. The female partner will also be followed to determine the outcome of the pregnancy. Information on the status of the mother and child will be forwarded to the sponsor. Generally, the follow-up will be no longer than 6 to 8 weeks following the estimated delivery date. Any termination of the pregnancy will be

reported regardless of fetal status (presence or absence of anomalies) or indication for the procedure.

Female Participants who become pregnant/breastfeed

The investigator will collect pregnancy information on any female participant who becomes pregnant or breastfeeds during treatment and 30 days after GC4711/placebo. Information will be recorded on the appropriate form and submitted to the sponsor within 24 hours of learning of a participant's pregnancy.

The participant will be followed to determine the outcome of the pregnancy. The investigator will collect follow-up information on the participant and the neonate, and the information will be forwarded to the sponsor. Generally, follow-up will not be required for longer than 6 to 8 weeks beyond the estimated delivery date. Any termination of pregnancy will be reported, regardless of fetal status (presence or absence of anomalies) or indication for the procedure.

A spontaneous abortion (occurring at < 22 weeks gestational age) or still birth (occurring at > 22 weeks gestational age) is always considered to be an SAE and will be reported as such.

Any female participant who becomes pregnant while participating in the study will discontinue study intervention.

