Inclusion and exclusion criteria ^e	X									
Registration/Randomization (Phase 1/Phase 2) ^e	X									
Medical history (includes smoking history)	X									
Demography	X									
Complete PE including height and weight	X								X	
ECOG Performance Status	X								X	
Vital signs ^f	X	X	X	X	X	X				
PK Blood samples ^g		X	X							
12-lead ECG ^h	X	X		X						
AE/SAE review ⁱ		X	X	X	X	X	X	X	X	
Concomitant medications/treatments and smoking review ^j	X	X	X	X	X	X		X	X	X
Survival Status								X	X	X
Serum pregnancy test (WOCBP only)	X									
Serum chemistry panel	X						X			
Complete blood count	X						X		X	
PT/INR, aPTT	X									
PFTs – SpO ₂ , FEV1, FVC and DLCO ^{k, n}	X								X	
CT chest for pneumonitis scoring ^k	X								X	X
CT (chest, abdomen, pelvis) ^k	X								X	X
GC4711/Placebo IV infusion ^l		X	X	X	X ^l	X ^l				
SBRT administration ^m		X	X	X	X ^m	X ^m				

AE = adverse event, BP = blood pressure, CBC = complete blood count, CT = computed tomography, CTCAE = Common Terminology Criteria for Adverse Events, DLCO = diffusion capacity of lung for carbon monoxide, ECG = electrocardiogram, ECOG PS = eastern cooperative oncology group performance status, FEV1 = forced expiratory volume in 1 second, FU = Follow-up, , IV = intravenous, PE = physical examination, PET = positron emission tomography, PFTs = pulmonary function tests, PK = pharmacokinetics, SAE = serious adverse event.

- a Screening evaluations should occur within 21 days of Treatment Day 1, except where otherwise noted
- b The Day 12 visit should occur 7 days after the last dose of SBRT \pm 5 days
- c The 30- and 90- day post SBRT completion visits should occur on or within 7 days after target date and may be performed remotely via telemedicine visits. The Months 6 and 12 post SBRT completion visits should occur \pm 7 days of target date.
- d The Month 18 and 24 post SBRT visits should occur \pm 14 days of target date.
- e Registration/Randomization should occur after all screening assessments are performed, eligibility is confirmed, and within 7 days of the first dose of SBRT. Confirmation of eligibility should include confirmation of diagnosis, histology and exclusion of distant disease by standard practice.
- f BP and HR should be taken prior to each infusion, monitoring possible hypotensive symptoms, please repeat before going from infusion to radiation site.

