5.1 Inclusion Criteria

Participants are eligible to be included in the study only if all the following criteria apply:

1. Male or female subjects at least 18 years of age.
2. Ability to understand and the willingness to sign a written informed consent.
3. Histological or biopsy proven NSCLC. For peripheral lesions, cytology and/or clear imaging-guided suspicion is accepted if histology cannot be obtained.
4. ECOG performance status of 0-3.
5. Lymph node negative (T1 to T3N0M0), centrally located (within 2cm in all directions around the proximal bronchial tree, including ultra-central tumors, abutting the bronchial tree or trachea) or large (>1-7cm) Non-Small Cell Lung Cancer (NSCLC) , judged acceptable for SBRT by the treating Investigator. Staged with FDG-PET/CT, brain CT or MRI with contrast and/or mediastinoscopy, measurable disease as defined by RECIST 1.1. (See Figure 2 below).
6. Adequate end-organ function, based on routine clinical and laboratory workup:
 - a. ANC >1,000 cells/ μ l, Platelets \geq 75,000 cells/ μ l, Hemoglobin \geq 8.0 g/dl
 - b. Serum creatinine \leq 2 mg/dL or calculated creatinine clearance \geq 30 ml/min
 - c. Total bilirubin \leq 1.5 x ULN (or direct bilirubin below the ULN), AST and ALT \leq 2.5 x ULN
 - d. International normalized ratio (INR) (or prothrombin time (PT)) and activated partial thromboplastin time (aPTT) \leq 1.5 x ULN unless participant is receiving anticoagulant therapy, if values are within the intended therapeutic range
7. Males and females of must agree to use effective contraception starting prior to the first day of treatment and continuing after the last dose of GC4711/Placebo for 30 days (females) and 90 days (males).

[figure not shown]

Figure 2 Anatomy of central and ultra-central lung tumors

Timmerman and colleagues defined central lung tumors as those located within 2 cm of the proximal bronchial tree (Timmerman 2006). Here defined ultra-central lung tumors as those abutting the proximal bronchial tree or trachea (Lo 2010, Chaudhuri 2015, Chang 2018).

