5.4 Discontinuation of Study Intervention and Participant Discontinuation/Withdrawal

Subject Study Withdrawal: A subject has the right to withdraw from the study at any time for any reason. Subjects who withdraw consent from study treatment and/or study assessments early should be encouraged to continue with survival and late toxicity follow-up, if feasible.

Subject Study Discontinuation: The Investigator or Sponsor may also, at his/her discretion, discontinue a subject from participating in this study at any time.

Study Intervention Discontinuation: A subject may discontinue study treatment but remain in the study for follow-up for any of following reasons:

- A protocol violation (reason must be specified, for example: lack of compliance, use of a prohibited concomitant medication, failure to meet inclusion/exclusion criteria after study entry, etc.)
- The subject was “lost to follow-up”
- Unacceptable adverse event necessitating treatment cessation
- More than three infusion modifications of GC4711/placebo
- Subject requests to withdrawal from the study treatment
- Subject becomes pregnant
- Other reasons (reason must be specified, for example: the subject moved, investigator decision, Sponsor decision to terminate trial, etc.)

If a subject discontinues from the study treatment early (did not complete SBRT regimen and/or receive all protocol required infusions of study drug), they will continue to be followed for progression, toxicities and survival as outlined in the SOA.

The primary reason and date for ceasing treatment, discontinuation and/or subject withdrawal will be clearly documented in the subject's medical record and recorded on the appropriate CRF page.

Discontinuation of specific study sites or of the study are handled as part of

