Appendix 1.

6 INVESTIGATIONAL PRODUCT AND TREATMENT OF SUBJECTS

Study intervention is defined as any investigational intervention(s), marketed product(s), placebo, or medical device(s) intended to be administered to a study participant according to the study protocol.

Refer to the GC4711 IB and Pharmacy Manual for more detailed information regarding the storage, preparation, destruction, and administration of each treatment.

The site pharmacists will be unblinded to the treatment assignments. The Principal Investigator and remainder of the site staff will be blinded to treatment assignment. The Unblinded Pharmacist should take every precaution to prepare the study treatment in a blinded fashion and out of site from the Blinded site clinical staff. The Blinded Clinical Staff should be mindful of the steps in place to maintain the blind.

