7.3 Pregnancy

The risks of treatment with GC4711 during pregnancy have not been evaluated. Male subjects and female subjects of childbearing potential who engage in sexual intercourse should use a barrier method of contraception throughout the study and for 30 days (females) or 90 days

(males) following the last dose of GC4711/Placebo. If a pregnancy is reported, the investigator should inform the sponsor within 24 hours of learning of the pregnancy and should follow the procedures outlined in Appendix 6.

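### The only scheduled pregnancy test may be 14 to 21 days old at randomisation, and the passages on contraception and on stopping for pregnancy need reconciling

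*Combined protocol and SAP*

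**What the plan says.** **Eligibility and testing.** Exclusion 11 in Section 5.2 bars women who are pregnant or breastfeeding. Table 1 (Schedule of Activities) has one row for a serum pregnancy test in women of childbearing potential, marked in the Screening column only. The row carries no footnote of its own, so footnote a governs it: "Screening evaluations should occur within 21 days of Treatment Day 1, except where otherwise noted". Footnote e requires randomisation to follow completed screening, once "eligibility is confirmed, and within 7 days of the first dose of SBRT".

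**Contraception.** Under inclusion criterion 7 in Section 5.1, participants "must agree to use effective contraception starting prior to the first day of treatment". Section 7.3 says that "The risks of treatment with GC4711 during pregnancy have not been evaluated" and goes on to say that sexually active participants should use a barrier method for the whole study and for 30 days (females) or 90 days (males) after the last dose. Section 4.2 counts the 21-day screening period in a participant's time on study.

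**Stopping.** Appendix 5 states: "Any female participant who becomes pregnant while participating in the study will discontinue study intervention". Section 5.4 includes pregnancy in a list introduced by "A subject may discontinue study treatment but remain in the study for follow-up for any of following reasons".

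**The concern.** Pregnancy status can change during screening. The plan treats it as an exclusion and as a reason to stop, yet lets the eligibility decision rest on a result that may be three weeks old at first dose. The protocol has a nearer checkpoint in footnote e, but does not require the pregnancy result to be current there.

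At stake is exposure of a pregnant participant to an investigational drug whose risks in pregnancy are unevaluated, together with SBRT. The other issue is uniform conduct. A site that learns of a pregnancy mid-course finds one passage that requires stopping and another that permits it, and neither says whether the rest of the radiation course is included. Two sites could read the same protocol and act differently.

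**Working it through.** There is no figure in the plan to reproduce. The check is calendar arithmetic followed by a comparison of passages.

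**Inputs**
- Earliest permitted test: 21 days before Day 1 (Table 1, footnote a).
- Randomisation: r days before first SBRT, with r from 0 to 7 (footnote e).
- Last dosing day L: Day 3 or Day 5 if 3 or 5 fractions are given on consecutive days. It is Day 10 at the general limit, Day 13 with the +3 allowance (Section 6.2 on SBRT) and Day 15 with the +5 allowance (Table 1, footnote m). The two allowances differ in the documents, so both are shown. Day 1 counts as the first calendar day.

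**Age of the result at randomisation** = 21 − r
- r = 7: 21 − 7 = 14 days
- r = 0: 21 − 0 = 21 days

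**Age of the result at the last dose** = 21 + (L − 1)
- L = 3: 23 days
- L = 5: 25 days
- L = 10: 30 days
- L = 13: 33 days
- L = 15: 35 days

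These ages are for a test on the earliest permitted date; a later draw shortens each one day for day. No scheduled pregnancy test falls within any of these intervals.

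**Does the plan tighten the window elsewhere?** Footnote a allows for exceptions, and the plan uses that: footnote k accepts standard-of-care imaging from within 56 days. The pregnancy row has no such entry. Footnote e names diagnosis, histology and exclusion of distant disease as things that confirmation of eligibility should include; it does not name pregnancy.

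**Contraception passages**
- Section 5.1: effective contraception, starting at an unstated time before Day 1.
- Section 7.3 with Section 4.2: a barrier method, worded as should, throughout a study period that includes screening.
- They differ on start and on method, and neither ties the start to the date of the test.

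**Stopping passages**
- Appendix 5: mandatory, object is study intervention.
- Section 5.4: permissive, object is study treatment. Its closing paragraph describes early discontinuation as not completing SBRT, not receiving all infusions, or both.
- Neither says whether pregnancy stops the infusions alone or the remaining SBRT fractions too.

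**Cross-reference.** Section 7.3 sends the reader to Appendix 6 for pregnancy procedures. Appendix 6 is the abbreviation list; the procedures are in Appendix 5.

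**The case against.** The strongest reply is that other controls exist. Exclusion 11 is not limited to the screening result. Appendix 2 lets the investigator order further tests at any time. Appendix 5 asks for additional evaluation to be considered when fertility is unclear before first dose. This is true and lowers the risk, but none of it is a scheduled check, and none makes the pregnancy result current when eligibility is confirmed. (The absence of a pregnancy test from the Appendix 2 table shows nothing, since that table also omits the screening test that Table 1 schedules.)

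A reader might infer that no contraception is required between the test and the first dose. The documents do not support that. Criterion 7 requires a start before Day 1, and Section 7.3 read with Section 4.2 can cover screening. What remains is that the start and method are stated inconsistently.

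A reader might also infer that the stopping rule cannot act. No scheduled test would trigger it, but it applies if a pregnancy becomes known in another way, such as participant report or an unscheduled test. Aligning the existing test with the eligibility checkpoint improves the entry decision; it does not make the rule detect pregnancies during treatment.

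It is tempting to add Sections 6 and 6.4 to the conflict. Section 6 gives a generic definition, "Study intervention is defined as any investigational intervention(s), marketed product(s), placebo, or medical device(s) intended to be administered to a study participant", that names neither GC4711 nor SBRT. Section 6.4 on SBRT continuing after infusions stop concerns infusion toxicity. Neither contradicts the pregnancy passages, though neither settles the scope.

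Finally, the permissive wording in Section 5.4 introduces a mixed list that includes loss to follow-up and adverse events that force cessation, so it may be meant as a list of categories and not as a grant of discretion. That is a fair reading, but a site should not have to infer it.

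**Conclusion.** The point holds as a safety and consistency correction. Exclusion 11 may rest on a pregnancy result that is 14 to 21 days old at randomisation and 23 to 35 days old at the last dose, assuming the earliest permitted draw. The contraception passages disagree on start and method. The stopping passages disagree on whether stopping is mandatory and leave its scope open.

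The expected number of affected participants cannot be derived. The documents give neither the number of women of childbearing potential among the approximately 71 participants nor a chance of conception. The number is probably small in this population and may be zero.

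No sample size, interval or analysis changes. A participant whose course was cut short after at least one dose would stay in the modified intent-to-treat population (Section 8.3); that is ordinary handling and not a fault. The case for acting is that the possible harm is serious and the correction is almost free.

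**What to change.** - **Table 1.** Reconcile the timing of the existing single pregnancy test with exclusion 11 and with footnote e, so that the eligibility decision rests on a result that is current at that checkpoint. The sponsor's clinical team decides what counts as current.
- **Sections 5.1 and 7.3.** State one rule on when contraception starts and which method is meant.
- **Section 5.4 and Appendix 5.** State one rule on whether stopping for pregnancy is mandatory, and say whether it covers the infusions, the remaining SBRT fractions or both. The clinical team decides which.
- **Section 7.3.** Change the reference from Appendix 6 to Appendix 5.

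The cost is a footnote and a few lines of wording in an amendment, with no added test. The one practical downside is that some women would have the test drawn later in screening than they otherwise would.
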